11.1 RADIOTRACERS: FDA-approved Volumex (Iodinated I-131 Albumin)

If an **exemption from IND filing requirements** is sought for a clinical investigation of a drug product that is lawfully marketed in the United States, review the following categories and complete the category that applies:

Exempt Category 1: The clinical investigation of a drug product that is lawfully marketed in the United States can be exempt from IND regulations if all of the following are yes:

- 1) The intention of the investigation is NOT to report to the FDA as a well-controlled study in support of a new indication for use or to be used to support any other significant change in the labeling for the drug. **YES**
- 2) The drug that is undergoing investigation is lawfully marketed as a prescription drug product, and the intention of the investigation is NOT to support a significant change in the advertising for the product. **YES**
- 3) The investigation does NOT involve a route of administration or dosage level or use in populations or other factor that significantly increases the risks (or decreases the acceptability of the risks) associated with the use of the drug product. **YES**
- 4) The investigation will be conducted in compliance with the requirements for institutional (HIC) review and with the requirements for informed consent of the FDA regulations (21 CFR Part 50 and 21 CFR Part 56). **YES**
- 5) The investigation will be conducted in compliance with the requirements regarding promotion and charging for investigational drugs. **YES**

11.2 Drugs/Biologics: Background Information on Study Medications and Tracers

	Previous Human Use	Known risks	Study Dose (x 2 Visits)	General Dose Range	Route of Admin
Lysine Chloride	Lysine Chloride has been used in a multitude of human studies, including a preliminary study with 11 patients at Yale involving supplementation with 21 grams/day of Lysine Chloride, with no adverse events reported (HIC)	May cause nausea, abdominal pain and diarrhea.	165 mmol/day (30.1 g/day)	1 gram 2X/day	PO (powder)

Volumex (Iodinated I-131 Albumin)	FDA-approved radio-pharmaceutical for the determination total blood & plasma volumes studies. & protein turnover	Immune virtually unaltered by iodination process, but an allergic reaction could occur after multiple dose	1.0cc (up to 25 microcuries)	blood & plasma volume studies = 0.2cc-2.0cc	IV-Push
--	--	--	------------------------------	---	---------

Iothalamate Meglumine*	Non- isotopic (cold) contrast agent. Cost effective tracer to measure GFR, allowing researchers to avoid exposing patients and themselves to isotopes.	Most frequently: nausea, vomiting, facial flush and a feeling of body warmth but generally occur at far higher doses than used in current study.	1 ml	30-60 ml	IV
Iohexol*	Cost effective tracer to measure GFR, allowing researchers to avoid exposing patients and themselves to isotopes	Contrast induced kidney injury pain, vision abnormalities including blurred vision, headache, taste perversion, arrhythmias including premature ventricular contractions (PVCs) and premature atrial contractions (PACs), angina/chest pain, nausea	1 ml	50 ml-200 ml	IV
D₂O	Standard reagent used in common clinical technique to determine TBW.	Naturally occurring, stable isotope of hydrogen found in all tap water. Known to be a safe, non-radioactive technique. Exact toxicity amount not determined; animal studies have shown D ₂ O concentrations must reach 30-35% of TBW to exert toxic effects (required dose would be ~15L for a 70kg patient).	10.0 grams	9-11mg	PO (liquid)

Potassium Iodide**	Used to block thyroidal uptake of radioactive isotopes of iodine.	Can cause arrhythmias, confusion, fatigue, fever, numbness, tingling, hyperthyroidism (prolonged use), hypothyroidism (prolonged use), diarrhea, nausea, vomiting, eosinophilia, lymphedema, hypersensitivity reaction, arthralgia, weakness, dyspnea, wheezing.	130 mg	130 mg	PO (Liquid)
Dextrose 5 % Fluid	FDA approved nonpyrogenic salt free solution for fluid and calorie replenishment for intravenous administration	Can cause fluid retention, hyperglycemia or hyperosmolar hyperglycemic state, hyponatremia, hypophosphatemia, hypersensitivity reactions and refeeding syndrome	200ml	500ml-1000ml	IV
Imodium AD or Imodium***	FDA approved to treat diarrhea	Can cause dizziness, drowsiness and Tiredness	Taken only is the participant experience diarrhea after taking Lysine Chloride/ placebo.	Maximum dose 16 mg /day	PO

* Iothalamate or Iohexol will only be administered to patients without a contrast dye allergy

**Potassium Iodide will be offered to patients under 40 to further reduce the radiation risks of Volumex to the thyroid.

*** Imodium will only be administered to participants who experience loose stools and are randomized on the study medication.

**** Unforeseen changes in the treatment plan may preclude the study team from continuing with study procedures after the iothalomate/iohexol and D2O are given. In this case the team may plan to initiate study on a subsequent day and administer an additional dose of iothalomate/iohexol and D2O on that day.

Iodide will be sourced from YNHH IDS. The Volumex will be sourced from the Daxor Corporation.

11.3 Is the drug provided free of charge to subjects? Yes, by the research group

11.4 Storage, Preparation & Use: Study medications will be stored by and obtained from YNHH IDS.

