Preliminary data with relevance to all aims: A pilot study of sodium free chloride administration was performed in 10 stable HF outpatients.^{2, 52} The primary purpose of the pilot was to determine feasibility, to ensure volume status wouldn’t worsen with the chloride load (this was unlikely, but unknown), and to see if any biologic effects plausibly related to chloride dependent processes could be detected. Details of inclusion/exclusion have been previously published². Briefly, enrollment required a diagnosis of HF, a loop diuretic dose of ≥ 80 mg/day furosemide equivalents, clinical stability and optimal volume status per an advanced HF physician. The median diuretic dose in those enrolled was 160 mg/day and the median NT-proBNP was 298 pg/ml, indicating a euvolemic population on high dose diuretics. There was no specific inclusion related to serum chloride levels, but the median level was 98 mmol/L and all patients had a chloride ≤ 100 mmol/L. Seven grams of lysine chloride was administered three times a day, providing 115 mmol/day of sodium free chloride daily. 115 mmol/day chloride supplementation was chosen as this should approximately double daily chloride intake. Patients were instructed to consume a 2-gram sodium diet for the week prior to and during the intervention period. All diuretics and HF medications were maintained constant over the duration of the study.

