4.0 Study Design: We propose a multi-site, randomized, double blind, placebo controlled study of 200 patients with decompensated heart failure receiving treatment with IV diuretics for volume overload. Participants will be enrolled at Yale New Haven Hospital and St. Francis hospital. This study was designed to be more pragmatic than the outpatient study (HIC2000022016) proposed in a separate protocol, with a parallel group randomization to 7 days of therapy with either 115 mmol/day of lysine chloride or placebo. 115 mmol/day of lysine chloride was chosen as this represents a similar cumulative chloride load to the higher dose 5-day inpatient study (separate HIC application). The primary endpoint will be the change in blood volume from baseline to 7 days (the range of days may vary between 5-8 days to minimize missing data).

Due to the current pandemic of COVID-19 (SARS-CoV2) and to remain in place for the future, the number of days between the V1 and V2 may be shortened (less than 5 days). This will allow for the completion of the study while the patient remains admitted to the hospital. The shortened duration will be utilized if the patient will be discharged before the 5-8-day window and allowing for complete data collection in the safest way possible. Thus, potentially eliminating the need to bring the patient back as an outpatient to complete the V2 in times of a pandemic or reduced visit capacity.

We propose an additional study arm to be completed in up to 5 additional patients. This arm would be an open-label study in patients with decompensated heart failure receiving treatment with IV diuretics for volume overload. The proposed arm would consist of 7

days (5-8 days to minimize missing data) of therapy with 115 mmol/day of lysine chloride. Patients enrolled into this arm will undergo identical study procedures to the randomized arm, with the exception of receiving only lysine chloride.

i.1 Study Protocol

A: Study Visit 1

1. Patient Arrival & Enrollment

- a. **Enrollment:** Patients that meet inclusion/exclusion criteria will be approached during their admission at YNHH (York St 5-1, 5-2, 5-3, 5-4, 5-7, 58 or St. Raphael's Campus Verdi 5 East and Verdi 3 East). If they agree to participate, the patient will sign an Informed Consent form prior to any study procedures taking place.

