 - The participant will be instructed to inform their treating physician when inpatient and the study team (if discharged) of any abdominal upset, the Imodium will be built into the epic order set(PRN order) for the care team to administer. If the patient is discharged, the PI or sub- I will be notified, and it is deemed appropriate; The study team will provide the participant with the Imodium.
 - The participant will be assessed daily for additional or worsening unformed stools, if appropriate the patient will receive additional doses of Imodium according to the manufacturer's instructions in conjunction with approval from the treating physician(inpatient) or study PI or sub- I if (discharged).

- Imodium over the counter: initial: Take 2 tablets/ capsules (4 mg) once. May take 1 additional tablet/ capsules after another episode of unformed stool. Up to a maximum of (8) 2 mg tablets or capsules or 16mg daily.
- The study team will provide the over the counter Imodium (once the patient is discharged) and the study team will record the number of doses taken per day

Patient Discharge vi.1 Vital Signs: Vital signs are obtained at the end of the study visit prior to discharge, to ensure patient safety.

vi.2 Home Urine Collection: patients will be given 24-hour urine collection containers to continue collecting urine at home.

B: Daily Monitoring and Dose Adjustment If a patient has a serum bicarbonate level less than 22mmol/L at screening, a venous pH and basic blood chemistries will be obtained via iSTAT and/or YNHH laboratory each day during the study period. 1cc of blood will be drawn each day to perform the test. If the patient has been discharged from YNHH and these tests are indicated, additional safety visits will take place (up to 5). For all patients, the results of any safety tests will be reviewed by the study physician and study nephrologist ([name]). If necessary, the study drug dose will be adjusted to once daily or no doses. The standard dosage is twice a day.

C: Continued IV Diuretic Therapy: The patient will remain admitted until the treating practitioner feels the patient no longer requires IV therapy, at which point they will be transitioned to oral diuretics.

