- f. **Lysine Chloride:** Lysine Chloride is freely available to the public as a dietary supplement and food additive and is on the FDA Generally Recognized as Safe (GRAS) list. Every day we eat large quantities of lysine and chloride in our diet. No significant side effects are anticipated to occur from lysine chloride based on a multitude of animal and human studies done with this supplement and the brevity of this intake (8 days). There was a rare incidence of minor GI upset associated with taking lysine chloride as a supplement in some of these studies, including nausea, abdominal pain and diarrhea. However, no side effects necessitating the discontinuation of lysine chloride supplementation were reported.^{a, b, c, d} This research group previously performed a preliminary study with 11 patients involving supplementation of lysine chloride at 21 grams per day, with no adverse events reported (HIC #1308012508, minimal risk study). The doses of lysine chloride

administered in this study are higher than the majority of prior studies, which did not study patients with heart failure. As a result, new, unexpected, or exaggerated side effects are possible.

- i. **Acidosis:** One possible side effect that we will follow closely will be the buildup of acid in the patients' blood, a condition that in very severe cases can cause illness or even be fatal. This condition would slowly develop if it were to happen and thus we will closely monitor serum pH and bicarbonate over the course of the study to be sure this does not occur. Importantly, we did not see any evidence of acid buildup in our pilot study of heart failure patients where similar doses were used.
- ii. **Volume depletion:** An additional possibility is that lysine chloride will work "too well" in removing fluid which could cause dehydration and possible kidney damage. As a result, we will closely follow kidney function throughout the course of the study and adjust diuretics dosage and the study medication if too much fluid is removed.

References

- a. Rubin, A.L., et al., The Use of L-Lysine Monohydrochloride in Combination with Mercurial Diuretics in the Treatment of Refractory Fluid Retention. *Circulation*, 1960. 21(3): p. 332-336.
- b. Spencer, H., Samachson, J., 1963. Effect of lysine on calcium metabolism in man. *J. Nutr.* 81:301-6.

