Personnel responsible for the safety review and its frequency: The PI will be responsible for monitoring the data, assuring protocol compliance, and conducting the safety reviews at the specified frequency which must be conducted at a minimum of every 6 months (including when re-approval of the protocol is sought). During the review process, the PI (monitor) will evaluate whether the study should continue unchanged, require modification &/or amendment, or close to enrollment. Either the PI, the IRB, or the Yale Data Safety Monitoring Board (DSMB) have the authority to stop or suspend the study or require modifications.

The overall risk associated with the proposed study is deemed moderate for the following reasons: We believe there are minimal risks to the subjects from the lysine chloride and D₂O administered during the study. Lysine chloride is freely available to the public as a dietary supplement. No significant side effects are anticipated to occur from supplementing lysine chloride based on a multitude of animal and human studies done with this supplement and the brevity of this intake (8 days). This research group previously performed a preliminary study with 11 patients involving supplementation of lysine chloride at 21 grams per day, with no adverse events reported (HIC #1308012508). D₂O occurs naturally, is widely used in various water space studies, and is very well tolerated, especially in such small, one-time doses. Iothalamate and Iohexol have been used extensively in diagnostic radiology, and while it can cause transient nausea, vomiting, facial flushing and a feeling of body warmth, these side effects are typically only seen in much higher doses than that proposed for this study. We view the risks associated with collecting up to 105cc of blood during each Study Visit as moderate, as the proposed volume to be drawn is larger than the amount traditionally drawn for a basic complete count and chemistry. The IV radiolabeled albumin presents moderate risk to the study subjects. Each ultra-low dose proposed will be equivalent to whole body, uniform exposure of 0.1 rem of radiation, which is well below the dose guidelines established by the federal government, and adhered to by the YNHH Radiation Safety Committee for research subjects.

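### The drug table gives the lysine chloride study dose as 165 mmol/day, 43% above the 115 mmol/day that Study Design sets for both arms that receive it

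*Combined protocol and SAP*

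**What the plan says.** Section 4.0 (Study Design) describes a "parallel group randomization to 7 days of therapy with either 115 mmol/day of lysine chloride or placebo". It justifies the dose on the ground that "this represents a similar cumulative chloride load to the higher dose 5-day inpatient study", which it treats as a separate protocol. The open-label arm is given the same dose, 7 days (window 5 to 8) "of therapy with 115 mmol/day of lysine chloride".

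Section 4.0, part B (Daily Monitoring and Dose Adjustment) adds: "The standard dosage is twice a day". The only adjustment it allows is downward, to once daily or to none.

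Section 11.2 (Drugs/Biologics) tabulates each agent. In the lysine chloride row the Study Dose entry is "165 mmol/day (30.1 g/day"). The same row cites an earlier study at 21 g/day as its safety background.

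Two other places bear on the dose:

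- Section 3.0, preliminary data: "Seven grams of lysine chloride was administered three times a day, providing 115 mmol/day of sodium free chloride daily".
- Section 8.2, item f (Acidosis): "we did not see any evidence of acid buildup in our pilot study of heart failure patients where similar doses were used".

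**The concern.** The protocol states two different daily doses of its investigational drug. The question here is consistency; the choice of 115 mmol/day is not disputed.

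Section 4.0 expresses the dose in millimoles only. Someone who has to weigh out or order a powder needs grams, and the one gram figure labelled as this trial's dose is the 30.1 g/day in section 11.2. That section also covers preparation and the investigational pharmacy. A local ethics board, such as the one the second site must approach, could assess either dose depending on which section it read.

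The safety argument is tied to the lower figure. Acidosis is the risk section 8.2 treats most seriously, and its reassurance comes from a pilot at 21 g/day. Section 9.0 likewise relies on "supplementation of lysine chloride at 21 grams per day, with no adverse events reported". At 30.1 g/day that support would be weaker.

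**Working it through.** **Inputs**

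| Item | Value | Source |
|---|---|---|
| Dose, randomised and open-label arms | 115 mmol/day | Section 4.0 |
| Study Dose entry | 165 mmol/day, 30.1 g/day | Section 11.2 |
| Pilot dose | 7 g three times a day, 115 mmol/day | Section 3.0 |
| Frequency in this trial | twice a day, reducible only | Section 4.0, part B |
| Treatment length | 7 days, window 5 to 8; shorter in a pandemic or when visit capacity is reduced | Section 4.0 and its part E |

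**1. Reproduce the table entry.** The pilot gives 3 × 7 = 21 g for 115 mmol, so 21 / 0.115 = 182.6 g/mol. At that ratio 165 mmol is 0.165 × 182.6 = 30.1 g, which matches the entry. In reverse, 30.1 / 0.165 = 182.4 g/mol, and 0.115 × 182.4 = 20.98 g, or 21.0 g. The entry's two numbers therefore agree with each other. It is a coherent but different dose, neither a conversion error nor a garbled table cell.

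**2. Size of the gap**

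- In millimoles: 165 − 115 = 50 mmol/day; 165 / 115 = 1.435.
- In grams: 30.1 − 21.0 = 9.1 g/day; 30.1 / 21.0 = 1.433.
- Per administration, assuming two equal doses (the protocol does not say they are equal): 21.0 / 2 = 10.5 g against 30.1 / 2 = 15.05 g.

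**3. Cumulative chloride load (daily dose × days)**

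| Days | At 115 mmol/day | At 165 mmol/day | Difference |
|---|---|---|---|
| 5 | 575 mmol | 825 mmol | 250 mmol |
| 7 | 805 mmol | 1155 mmol | 350 mmol |
| 8 | 920 mmol | 1320 mmol | 400 mmol |

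Treatment may be shorter than 5 days in the circumstances noted above, so the 5-day row is not the permitted minimum. The ratio is the same at any duration.

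**4. Can the two figures be reconciled?**

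- *Another arm.* The open-label arm is the only other one, and it is also at 115.
- *Titration.* Section 4.0, part B and section 8.3, item f allow reduction only.
- *The column heading, which refers to two visits.* The entry is a per-day amount, and neither halving nor doubling 165 gives 115.

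None of these explains the gap.

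**5. Which figure is intended?** Section 4.0 gives 115 twice, with a reason, and describes the separate 5-day study as the one with the higher dose. The acidosis statement calls the pilot dose similar, and the pilot dose was exactly 115 mmol/day. The 165 may have been carried over from the 5-day study: 165 × 5 = 825 mmol against 115 × 7 = 805 mmol, a ratio of 1.025, which fits the stated matching of cumulative load. That is an inference, since the documents do not give that study's dose, and the conclusion does not depend on it.

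**The case against.** The strongest reply is that this is one stray entry in a background table. The operative design section states 115 mmol/day for both arms and says why. Entry limits on bicarbonate and venous pH (section 7.4), laboratory monitoring, and dose reduction at the study physicians' discretion (section 4.0, parts B and D; section 8.3) protect patients at either dose. No document shows a dosing error, and the statistics are untouched.

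More specific points can be added:

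- The pilot description in section 3.0 lets a reader convert 115 mmol to 21 g, so the table is not the only route to grams.
- The 21 g/day in the same table row makes the conflict visible.
- Section 8.2 already warns that doses here exceed most earlier studies and that unexpected effects may occur.
- Support from the pilot would be weakened at 1.43 times its dose, not cancelled, because no threshold for similarity is given.

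These specific points are fair and limit the likely harm. They do not remove the contradiction. The entry is headed as the study dose of the investigational product, so it is more than background. The safeguards respond to laboratory changes after dosing and do not settle what to dispense. Daily pH testing is specified only for patients whose screening bicarbonate is below 22 mmol/L.

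**Conclusion.** The concern holds. Sections 4.0 and 11.2 give different daily doses of the study drug, and no reading of the documents reconciles them. The table entry is higher by 50 mmol/day (9.1 g/day, 43%), or 350 mmol over seven days.

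That 115 mmol/day is the intended dose is a judgement from the weight of the text, and a strong one. The contradiction stands whichever figure is meant. The gram equivalents rest on the protocol's own pilot conversion, and the per-administration figures on an equal split. The consequence is for dispensing and for safety review. The sample size and the analysis are not affected, and there is no evidence of misdosing.

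**What to change.** Change the lysine chloride Study Dose entry in section 11.2 to 115 mmol/day (21.0 g/day). State the gram amount in section 4.0 as well, with the amount per administration; about 10.5 g twice daily follows if the doses are equal, which the sponsor should confirm. Check the pharmacy order set, the consent wording and the second site's submission against it.

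If 165 mmol/day is in fact intended, section 4.0 needs a new dose and a new cumulative-load rationale, and the acidosis statement in section 8.2 must stop describing the pilot doses as similar.

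The cost is one table entry, one added figure and a document check, with no change to sample size or analysis.

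Two clerical slips, which carry no weight in this point, can be corrected in the same amendment. The deuterium oxide amounts are in milligrams in section 8.2 and in the general dose range of section 11.2, where grams are meant. The potassium iodide dose is 135 mg in section 8.3 and 130 mg in section 11.2.
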